5 STUDY ENROLLMENT AND WITHDRAWAL

The study population will be representative of subjects with varying degrees of liver disease as defined by Child-Pugh scores. The Child-Pugh scores used for eligibility in the study will be calculated at screening only. The Child-Pugh score is based on five clinical measures of liver function: total bilirubin, serum albumin, prothrombin, ascites and hepatic encephalopathy. Based on their score patients are defined as mild (5-6 points), moderate (7-9 points), or severe (10-15 points). Approximately 36 subjects between the ages of 18 and 70 years will be enrolled over an estimated 9-month period. A subject is considered enrolled in this study once they have signed a study consent form, met all eligibility criteria, and have been admitted to the confinement/hospital unit on Admission Visit (Day -1).

Subjects with hepatic impairment for this study will be mainly identified at Duke University Health System Hospitals and Clinics and the Durham Veterans Administration Hospital as well as St Louis University. Non-hepatically impaired controls will be identified from the site-specific recruitment registries and the community. Subjects for this study may also be identified through advertisement, letters, and other forms of communication.

Subject Inclusion and Exclusion Criteria must be confirmed by a study clinician licensed to make medical diagnoses.

No exemptions are granted on Subject Inclusion/Exclusion Criteria in DMID-sponsored studies. Questions about eligibility will be directed toward the DMID Medical Officer.

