5.1 Eligibility Criteria

5.1.1 Subject Inclusion Criteria

Subjects must meet all of the following inclusion criteria in order to participate in the study:

Inclusion Criteria for Patients with Hepatic Impairment (Groups 1-3)

- 1) Subject is able to give voluntary written informed consent before any study related procedure is performed.
- 2) 18-70 years of age, inclusive.
- 3) Acceptable laboratory values* obtained at screening (within 21 days prior to admission to the confinement/hospital unit) and either at or within 72 hours of admission to the confinement/hospital unit.

**Chemistry, complete blood count, AST, ALT, total bilirubin, alkaline phosphatase, albumin, and urinalysis deemed not clinically significant by the investigator.*

- 4) Hepatic impairment classified as Child-Pugh class A (mild), B (moderate), or C (severe) criteria at screening for Groups 1, 2, or 3, respectively, and documented evidence of hepatic cirrhosis*.

**by biopsy, nuclear scan, CT, MRI, ultrasound, or other clinically acceptable methods*

- 5) If female, not of childbearing potential* or agrees to avoid becoming pregnant by using acceptable contraception** during the duration of the study.

**Non-childbearing potential is defined as being post-menopausal for at least 2 years, status after bilateral oophorectomy or status after hysterectomy.*

***Females of childbearing potential must agree to use two acceptable methods of contraceptives: bilateral tubal ligation; barrier method (condom) by the male partner (even if vasectomized); hormonal contraceptives; intrauterine contraceptive devices; diaphragm in combination with contraceptive jelly, cream, foam, or spermicide; and abstinence from sexual intercourse with men.*

- 6) If subject is male and capable of reproduction, agrees to avoid fathering a child for three months after dosing by using an acceptable method of birth control*.

**In addition to the use of a barrier method (condom) even if vasectomized, acceptable methods of birth control are restricted to a monogamous relationship with a woman who agrees to use acceptable contraception as outlined in inclusion criterion #5, and abstinence from sexual intercourse with women.*

- 7) If the subject is female, a negative serum pregnancy test at screening and a negative urine pregnancy test at admission to the confinement/hospital unit.

- 8) Willingness to comply with all protocol requirements.

Inclusion Criteria for Non-Hepatically Impaired Controls (Group 4)

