5.1.2 Subject Exclusion Criteria

Subjects meeting any of these exclusion criteria during screening (Visit 00A) will be excluded from study participation:

Exclusion Criteria for Patients with Hepatic Impairment (Groups 1-3)

- 1) Hypokalemia (< 3.5mEq/L), severe hypomagnesemia (< 1.1 mg/dL) or severe hypocalcemia (< 7.5 mg/dL).
- 2) AST or ALT > 10 times the upper limit of normal.
- 3) Creatinine clearance <60 ml/min.
- 4) Inability to swallow tablets.
- 5) Presence of any condition or finding* which would jeopardize subject safety, impact study result validity, or diminish the subject's ability to undergo all study procedures and assessments**.

**in the opinion of the site investigator*

***e.g., inability to draw PK samples*

- 6) History of fever or documented fever (oral temperature $\geq 100.4^{\circ}$ F or $\geq 38.0^{\circ}$ C) in the 48 hours prior to admission to the confinement/hospital unit.
- 7) Currently breastfeeding.
- 8) History of chronic tobacco/nicotine use (>10 cigarettes per day for 3 months minimum prior to admission).
- 9) History of clinically significant allergy or severe side effects with nitroimidazoles (e.g., Metronidazole and related substances and azole antifungals or aromatase inhibitors).
- 10) Receipt of an investigational drug, vaccine or biologic in a clinical trial within 30 days prior to screening.
- 11) Use of any over the counter (OTC) medication* within 7 days prior to admission to the confinement/hospital unit, unless** the substance would not likely impact the validity of the study results.

**including vitamins and herbal supplements, cough and cold medications.*

***in the opinion of the site investigator*

- 12) Treatment with CYP450 enzyme altering drugs* within 7 days prior to admission to the confinement/hospital unit, unless** the substance would not likely impact the validity of the study results.

**except hormonal contraceptives*

***in the opinion of the site investigator*

NOTE: See list of CYP450 enzyme altering drugs under the concomitant medications section [Table 6](#).

- 13) A positive blood screen for HIV.
- 14) A positive alcohol breath test (or other suitable test for alcohol) or a urine screen test for drugs of abuse* at screening and at admission to the confinement/hospital unit.

*Amphetamines, barbiturates, cocaine metabolites, marijuana, opiates, phencyclidine (PCP).

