8.6 Halting Rules

The study will be immediately suspended, and no additional doses administered if any of the following occurs:

1. *Any death occurring during the study that was not the result of trauma or accident.*
2. *2 or more hepatically impaired subjects experience a serious adverse event (other than death), related to study product.*
3. *2 or more non-hepatically impaired subjects experience a serious adverse event (other than death), related to study product.*
4. *3 or more subjects develop a severe (Grade 3) abnormality in the same laboratory parameter, regardless of relatedness to study product. Exception to this would be:*
 - a. *Grade 3 CK elevation without systemic complaints*
 - b. *If there are obvious and acceptable physiological explanations for a Grade 3 abnormality (e.g., Grade 3 hematuria in a menstruating female).*

In this case, the study will be suspended pending review and discussion of all appropriate study data by the Investigator, Sponsor or DMID Medical Monitor, the Independent Safety Monitor, and the Safety Monitoring Committee. The study will not be re-started until all parties have agreed to the course of action to be taken, the IRB and Food and Drug Administration (FDA) have been notified, and IRB approval is obtained.

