Appendix B. Child-Pugh System

Encephalopathy grade*	None or 0	1 or 2	3 or 4
Ascites	Absent	Slight	Moderate
Serum bilirubin (mg/dL)	< 2	2 - 3	> 3
Serum albumin (g/dL)	> 3.5	2.8 - 3.5	< 2.8
Prothrombin Time Prolongation (seconds over control)	< 4	4 - 6	> 6
or [INR]	(INR < 1.7)	(INR 1.7 - 2.3)	(INR > 2.3)
Points scored for observed finding	1	2	3

*Encephalopathy must be attributable to liver disease and graded according to present or historical data. If a subject with hepatic impairment is taking a pharmaceutical agent to control symptoms of liver disease (e.g., lactulose to reduce ammonia) the principal investigator may assign a score that is representative of the subject's status without pharmaceutical intervention. This action will be clearly documented in the source documents and approved by the Sponsor's medical monitor.

Grade 0: normal consciousness, personality, neurological examination, and electroencephalogram (EEG)

Grade 1: restless, sleep-disturbed, irritable/agitated, tremor, impaired handwriting, 5 cps waves on EEG

Grade 2: lethargic, time-disoriented, inappropriate, asterixis, ataxia, slow triphasic waves on EEG

Grade 3: somnolent, stuporous, place-disorientated, hyperactive reflexes, rigidity slower waves on EEG

Grade 4: unarousable coma, no personality/behavior, decerebrate, slow 2-3 cps delta activity on EEG.

Group	Cumulative Score	Child-Pugh Class	Description
1	5-6 points	A	Mild hepatic impairment
2	7-9 points	B	Moderate hepatic impairment
3	10-15 points	C	Severe hepatic impairment

References:

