Appendix C. Toxicity Tables

ABBREVIATIONS:

Abbreviations utilized in the Table:

ULN = Upper Limit of Normal	Req = Required	ADL = Activities of Daily Living
LLN = Lower Limit of Normal	Mod = Moderate	Dec = Decreased
Rx = Therapy	IV = Intravenous	

ESTIMATING SEVERITY GRADE

For abnormalities NOT found elsewhere in the Toxicity Tables use the scale below to estimate grade of severity:

- **GRADE 1: Mild** Transient or mild discomfort (< 48 hours); no medical intervention/therapy required
- **GRADE 2: Moderate** Mild to moderate limitation in activity - some assistance may be needed; no or minimal medical intervention/therapy required
- **GRADE 3: Severe** Marked limitation in activity, some assistance usually required; medical intervention/therapy required, hospitalizations possible

Clinical Adverse Events

VITAL SIGNS	Mild (Grade 1)	Moderate (Grade 2)	Severe (Grade 3)	
Fever (°C) **	38.0 – 38.4	38.5 – 38.9	≥ 39.0	** Oral temperature; no recent hot or cold beverages or smoking. A protocol should select either °C or °F for inclusion.
(°F) **	100.4 – 101.1	101.2 – 102.0	≥ 102.1	
Tachycardia - beats per minute	101 – 115	116 – 130	> 130 or ventricular dysrhythmias	
Bradycardia - beats per minute	50 – 54 or 45-50 bpm if pre-dose visit rate < 60 bpm	45 – 49 or 40-44 if pre-dose visit rate < 60bpm	< 45 or <40 bpm if pre-dose visit rate <60 bpm	
Hypertension (systolic)- mm Hg	141-150	151-160	> 160	Assume supine position for 10 min at rest in non-sleeping subjects; for

				adverse events, need three measurements on the same arm with concordant results.
Hypertension (diastolic) - mm Hg	91-95	96-100	> 100	
Hypotension (systolic) - mm Hg	85-89	80-84	< 80	
Tachypnea – breaths per minute	23-25	26-30	> 30	

CARDIOVASCULAR	Grade 1	Grade 2	Grade 3
Arrhythmia	Asymptomat ic, transient signs, no Rx required	Recurrent/persistent; symptomatic; Rx required	Unstable dysrhythmia; hospitalization and treatment required
Hemorrhage, Blood Loss	Estimated blood loss \leq 100 mL	Estimated blood loss $>$ 100 mL, no transfusion required	Transfusion required
QT/QTc prolongation	Male: 441-470 msec Female: 451-470 msec	Male: 471-500 msec Female: 471-500 msec:	> 500 msec OR > 60 msec change from admission visit

RESPIRATORY	Grade 1	Grade 2	Grade 3
Cough	Transient- no treatment	Persistent cough;	Interferes with daily activities

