Bronchospasm, Acute	Transient; no treatment; 71% - 80% FEV1 of peak flow	Requires treatment; normalizes with bronchodilator; FEV1 60% - 70% (of peak flow)	No normalization with bronchodilator; FEV1 $<$ 60% of peak flow
Dyspnea	Does not interfere with usual and social activities	Interferes with usual and social activities, no treatment	Prevents daily and usual social activity or requires treatment

GASTROINTESTINAL	Grade 1	Grade 2	Grade 3
Nausea	No interference with activity	Some interference with activity	Prevents daily activities
Vomiting	No interference with activity or 1 - 2 episodes/24 hours	Some interference with activity or > 2 episodes/24 hours	Prevents daily activity or requires IV hydration
Diarrhea	2 - 3 loose or watery stools or < 400 gms/24 hours	4 - 5 loose or watery stools or 400 - 800 gms/24 hours	6 or more loose or watery stools or > 800gms/24 hours or requires IV hydration

Laboratory Adverse Events			
Blood, Serum, or Plasma *	Mild (Grade 1)	Moderate (Grade 2)	Severe (Grade 3)
Potassium – Hypokalemia mmol/L	3.1 – <LLN	2.7 – 3.0	<2.7
Potassium – Hyperkalemia mmol/L	>ULN – 5.6	6. – 6.5	>6.5
Glucose – Hypoglycemia Fasting- mg/dL [#]	61 – <LLN	55 – <61	<55
Glucose – Hyperglycemia Fasting – mg/dL [#]	>ULN – 120	>120 – 130	>130
Blood Urea Nitrogen mg/dL	>ULN – 29	30 – 35	>35
Creatinine – mg/dL	>ULN – 1.7	1.8 – 2.0	>2.0
Calcium – hypocalcemia mg/dL	8.0 – <LLN	7.5 – 7.9	<7.5
Calcium – hypercalcemia mg/dL	>ULN – 11.0	11.1 – 11.5	>11.5
Magnesium – hypomagnesemia mg/dL	1.3 – <LLN	1.0 – <1.2	<1.0

Laboratory Adverse Events			
Blood, Serum, or Plasma *	Mild (Grade 1)	Moderate (Grade 2)	Severe (Grade 3)
Albumin – Hypoalbuminemia g/dL	2.8 – <LLN	2.5 – 2.7	<2.5
Alkaline phosphatase – U/L(Age 18 years)	>ULN – 240	241 – 360	>360
AST U/L	>ULN – 105	106 – 175	>175
ALT U/L	>ULN – 105	106 – 175	>175
Bilirubin (serum total) mg/dL	>ULN - 2.0	2.1 - 2.5	>2.5
Hemoglobin - g/dL	10.5 – <LLN	9.5 – 10.4	< 9.5
Hematocrit %	32.3 – <LLN	28.0 – 32.2	< 28.0
RBC Decrease (Female) X10 ¹² /L	3.61 – <LLN	3.14 – 3.60	< 3.14
RBC Decrease (Male) X10E6/uL X10 ¹² /L	3.89 – <LLN	3.28 – 3.88	< 3.28
WBC Increase X10 ⁹ /L	>ULN– 15.0	15.1 – 20.0	> 20.0
WBC Decrease X10 ⁹ /L	2.5 – <LLN	1.5 – 2.4	< 1.5

Laboratory Adverse Events			
Blood, Serum, or Plasma *	Mild (Grade 1)	Moderate (Grade 2)	Severe (Grade 3)
Lymphocytes Decrease - X10 ⁹ /L	0.5 – <LLN	0.3 – 0.4	<0.3
Neutrophils Decrease - X10 ⁹ /L	1.0 – <LLN	0.5 – 1.0	< 0.5
Monocytes Increased X10 ⁹ /L	>ULN-2.5	2.6-3.0	>3.0

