Eosinophils Increased X10 ⁹ /L	>ULN-0.75	0.76-1.50	>1.50
Basophils Increased X10 ⁹ /L	>ULN - 0.40	0.41-0.80	>0. 80
Platelets Decreased - X10 ⁹ /L	120 – <LLN	100 – 119	<100
INR	>ULN – 1.3	1.4 - 1.6	>1.6

Urine *	Mild (Grade 1)	Moderate (Grade 2)	Severe (Grade 3)
Protein	1+	2+	>2+
Glucose	Trace - 1+	2+	>2+

Blood (microscopic) - red blood cells per high power field (rbc/hpf)	3 - 10	11 - 50	>50 and/or gross blood
* The laboratory values provided in the tables serve as guidelines and are dependent upon institutional normal parameters.			
* Institutional normal reference ranges should be provided to demonstrate that they are appropriate.			

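### Halting rule 4 cannot count laboratory worsening in a subject who is already at Grade 3 on admission for that parameter

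*Protocol*

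**What the plan says.** Protocol Section 8.6, rule 4, stops dosing when "3 or more subjects develop a severe (Grade 3) abnormality in the same laboratory parameter, regardless of relatedness to study product". It is the only halting rule triggered by a laboratory value. Its exceptions are (a) isolated CK elevation without systemic complaints and (b) a Grade 3 value with an evident, acceptable physiological cause, illustrated by menstrual hematuria. Appendix C also removes fasting glucose from the halting criteria.

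Appendix C has three grades. Its laboratory rows are absolute; for example, the row "Bilirubin (serum total) mg/dL" puts Grade 3 above 2.5. Elsewhere the same appendix does use the subject's own starting value: Grade 3 QTc includes "> 60 msec change from admission visit", and bradycardia depends on the pre-dose rate. A footnote says "The laboratory values provided in the tables serve as guidelines and are dependent upon institutional normal parameters".

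Entry limits for Groups 1-3 are loose on liver tests. Inclusion criterion 3 asks for "Chemistry, complete blood count, AST, ALT, total bilirubin, alkaline phosphatase, albumin, and urinalysis deemed not clinically significant by the investigator", which sets no number and does not list INR. Transaminases exclude a subject only for "AST or ALT > 10 times the upper limit of normal". There is no numeric limit on bilirubin, albumin, INR or platelets.

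**The concern.** The study deliberately enrols people whose bilirubin, albumin and INR are abnormal, and then applies a halting rule built on absolute cut-offs for those tests. A subject who starts beyond a cut-off cannot newly reach it. With no Grade 4 and no change term, further deterioration in that test has no way into the rule 4 count.

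The automatic laboratory trigger is therefore weakest in the subjects with the worst starting liver function. The risk discussion in Protocol Section 2.3.1 lists drug holding rules for liver toxicity among the FDA's recommendations and says that this design meets them. Rule 4 also applies regardless of relatedness, so the other halting rules do not replace it one for one.

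**Working it through.** The documents give no operating characteristic for the halting rule, so there is no plan figure to reproduce. The check sets the Grade 3 cut-offs against what entry allows.

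**Step 1. Can an eligible subject start at Grade 3?**

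| Test | Grade 3 (Appendix C) | What entry allows | Lowest Child-Pugh score compatible with Grade 3 |
|---|---|---|---|
| INR | >1.6 | <1.7, 1.7-2.3, >2.3 score 1, 2, 3 points (Appendix B) | 5 (class A): a value above 1.6 but below 1.7 scores 1 point |
| Bilirubin, mg/dL | >2.5 | <2, 2-3, >3 score 1, 2, 3 points | 4 + 2 = 6 (class A) |
| Albumin, g/dL | <2.5 | >3.5, 2.8-3.5, <2.8 score 1, 2, 3 points | 4 + 3 = 7 (class B) |
| AST/ALT, U/L | >175 | up to 10 x ULN | any |
| Platelets, x10⁹/L | <100 | no limit | any |

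For AST/ALT, 10 x ULN exceeds 175 whenever ULN is above 17.5. With an assumed ULN of 35-40, entry is allowed up to 350-400 U/L, while Grade 3 begins at 175/40 = 4.4 to 175/35 = 5.0 x ULN.

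The gap does not reach every test. Exclusion criterion 1 removes potassium below 3.5, magnesium below 1.1 and calcium below 7.5 at screening. Grade 3 low values of these (<2.7, <1.0 and <7.5) therefore cannot be present then.

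**Step 2. How far does class membership overlap Grade 3?** I listed all Child-Pugh point patterns with encephalopathy at 1-2 points and the clotting item scored by INR. There are 6 patterns in class A, 75 in B and 81 in C.

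- INR at 2 or 3 points (at least 1.7, so Grade 3): 1 of 6, 40 of 75 and 67 of 81. In the rest (35 in class B, 14 in class C), Grade 3 INR is not implied.
- Bilirubin at 3 points (above 3, so Grade 3): 0 of 6, 14 of 75 and 40 of 81.

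With all encephalopathy scores, INR gives 45 of 90 (B) and 116 of 147 (C), and bilirubin 15 of 90 and 66 of 147. Bilirubin at 2 points and albumin at 3 points straddle their cut-offs and are not counted.

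These are score patterns given equal weight, not patient frequencies. Appendix B also lets clotting be scored in seconds of prothrombin time. In addition, "The Child-Pugh scores used for eligibility in the study will be calculated at screening only", so admission values may differ.

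**Step 3. What does rule 4 do with such a subject?** INR 1.6 is Grade 2 and 1.7 is Grade 3, so a move from 1.6 to 1.7 is a new Grade 3 and counts. INR 1.8 and 3.5 are both Grade 3, so a move from 1.8 to 3.5 is no change of grade and does not count.

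**Step 4. When does this disable the trigger within a group?** The rule needs three counting subjects. If 4 of the 6 planned in Group 3 enter at Grade 3 for a test, 6 - 4 = 2 remain who can count. For Groups 2 and 3 together, 12 - 10 = 2. The rule pools all of about 36 subjects, so Group 1 and the controls can still count.

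**Step 5. Does the SAP close the gap?** No. SAP Section 9.6 and its table shells give severity by time point, maximum post-baseline severity, change from baseline, and low/normal/high shift tables. These describe worsening but do not feed the halting count.

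**The case against.** The best defence is that rule 4 is a coherent new-onset rule and that worsening is handled elsewhere. Clinically significant worsening of an existing abnormality is an adverse event (Protocol Sections 8.1.1 and 8.3). If medically important it is an SAE (8.1.2), reported within 24 hours and copied to the independent safety monitor (8.3.1), who reviews SAEs in real time (8.7.1). Two related SAEs in impaired subjects halt the study under rule 2. The first SMC review is completed before Groups 2 and 3 open, and both reviews include laboratory data (10.5.1). The SMC charter and the MOP are not in the documents and may set counting conventions. Much of this stands, and it is why the gap is limited. It does not remove the gap: rule 2 needs relatedness and seriousness, the monitor sees other adverse events only as needed, and dosing may continue during the second SMC review.

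A reader might infer something stronger: that three unchanged admission values could suspend the study. The documents do not support that as the natural reading. The verb in rule 4 is *develop*, Section 8.3 treats a condition present at screening or admission as pre-existing unless it worsens, and exception (b) offers a way to excuse such values, although cirrhosis is not named.

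The guideline footnote in Appendix C leaves room for grading judgement, but it supplies no rule for worsening from admission. It is also fair that counting unrelated change in advanced cirrhosis could cause halts from fluctuation; the thresholds have to deal with that.

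**Conclusion.** The point holds as a limited gap in the automatic trigger. For any test already at Grade 3 before dosing, rule 4 cannot register further deterioration in that subject. Where the pre-dose value is below Grade 3, the rule works as written.

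The size in practice is unknown, because the documents do not say how many subjects will enter at Grade 3. The pattern counts show that overlap is built into the definitions of classes B and C. They should not be taken to mean that 67 in 81 severe subjects will have a Grade 3 INR.

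Nor do the documents support an inference that worsening would go unseen or that risk is high. Each subject gets one dose, so a halt protects only later subjects. The fatal liver injuries described in the Protocol occurred on a three-drug regimen, with onset at 21-24 days. For ALT, the rule operates normally unless the subject enters above 175 U/L. The primary PK estimates are unaffected.

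The conclusion rests on reading *develop* as new onset and on the absence of a counting rule in the SMC charter or MOP.

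**What to change.** Amend Section 8.6, rule 4, so that for each laboratory parameter a subject counts if either:

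1. the last pre-dose value was below Grade 3 and a post-dose value is Grade 3; or
2. the last pre-dose value was already Grade 3 and a post-dose value has worsened from it by a numeric change written into Section 8.6, given separately for INR, bilirubin, albumin, AST, ALT and platelets.

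Add one line saying that unchanged admission values do not count, and keep exceptions (a) and (b). The last pre-dose value matches the baseline in SAP Section 6.1. The wording also settles the subject who dips to Grade 2 and returns to the starting level: that subject does not count.

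The medical monitor and SMC should agree the numbers before the next Group 2 or 3 dose and set them above ordinary fluctuation. The documents give no basis for proposing specific values here.

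The cost is one amendment with IRB approval, six thresholds and one programmed flag. Admission, Day 2, Day 5 and Day 12 values are already collected, so no samples or subjects are added. The downside is a possible halt from disease fluctuation if a threshold is too small.
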